4.5.6 Treatment of Nivolumab- or Ipilimumab-Related Infusion Reactions

Since nivolumab and ipilimumab contain only human immunoglobulin protein sequences, each is unlikely to be immunogenic and induce an infusion or hypersensitivity reaction. However, if such a reaction were to occur, it might manifest with fever, chills, rigors, headache, rash, pruritis, arthralgias, hypo- or hypertension, bronchospasm, or other symptoms. All Grade 3 or 4 infusion reactions should be reported within 24 hours to the BMS Medical Monitor and reported as an

SAE if criteria are met. Infusion reactions should be graded according to NCI CTCAE (version 4.0) guidelines.

Treatment recommendations are provided below and may be modified based on local treatment standards and guidelines as appropriate:

For Grade 1 symptoms (Mild reaction; infusion interruption not indicated; intervention not indicated):

Remain at bedside and monitor subject until recovery from symptoms. The following prophylactic premedications are recommended for future infusions: diphenhydramine 50 mg (or equivalent) and/or paracetamol 325 to 1000 mg (acetaminophen) at least 30 minutes before additional nivolumab or ipilimumab administrations.

For Grade 2 symptoms (Moderate reaction requires therapy or infusion interruption but responds promptly to symptomatic treatment [eg, antihistamines, non-steroidal anti-inflammatory drugs, narcotics, corticosteroids, bronchodilators, IV fluids]; prophylactic medications indicated for ≤ 24 hours):

Stop the nivolumab or ipilimumab infusion, begin an IV infusion of normal saline, and treat the subject with diphenhydramine 50 mg IV (or equivalent) and/or paracetamol 325 to 1000 mg (acetaminophen); remain at bedside and monitor subject until resolution of symptoms. Corticosteroid or bronchodilator therapy may also be administered as appropriate. If the infusion is interrupted, restart the infusion at 50% of the original infusion rate when symptoms resolve; if no further complications ensue after 30 minutes, the rate may be increased to 100% of the original infusion rate. Monitor subject closely. If symptoms recur then no further nivolumab or ipilimumab will be administered at that visit. Administer diphenhydramine 50 mg IV, and remain at bedside and monitor the subject until resolution of symptoms. The amount of study drug infused must be recorded on the electronic case report form (eCRF). The following prophylactic premedications are recommended for future infusions: diphenhydramine 50 mg (or equivalent) and/or paracetamol 325 to 1000 mg (acetaminophen) should be administered at least 30 minutes before additional nivolumab or ipilimumab administrations. If necessary, corticosteroids (recommended dose: up to 25 mg of IV hydrocortisone or equivalent) may be used.

For Grade 3 or Grade 4 symptoms (Severe reaction, Grade 3: prolonged [ie, not rapidly responsive to symptomatic medication and/or brief interruption of infusion]; recurrence of symptoms following initial improvement; hospitalization indicated for other clinical sequelae [eg, renal impairment, pulmonary infiltrates]; Grade 4: (life threatening; pressor or ventilatory support indicated):

Immediately discontinue infusion of nivolumab or ipilimumab. Begin an IV infusion of normal saline, and treat the subject as follows. Recommend bronchodilators, epinephrine 0.2 to 1 mg of a 1:1,000 solution for subcutaneous administration or 0.1 to 0.25 mg of a 1:10,000 solution injected slowly for IV administration, and/or diphenhydramine 50 mg IV with methylprednisolone 100 mg IV (or equivalent), as needed. Subject should be monitored until the

investigator is comfortable that the symptoms will not recur. Nivolumab or ipilimumab will be permanently discontinued. Investigators should follow their institutional guidelines for the treatment of anaphylaxis. Remain at bedside and monitor subject until recovery from symptoms. In the case of late-occurring hypersensitivity symptoms (eg, appearance of a localized or generalized pruritis within 1 week after treatment), symptomatic treatment may be given (eg, oral antihistamine, or corticosteroids).

4.5.7 Treatment Beyond Disease Progression

As described in [Section 1.1.11](#) accumulating evidence indicates that subjects treated with immunotherapy may derive clinical benefit despite evidence of PD.⁸⁴

Subjects will be permitted to continue with treatment beyond initial RECIST 1.1 defined PD as long as they meet the following criteria:

- Investigator-assessed clinical benefit and
- Subject is tolerating study drug.

The assessment of clinical benefit should take into account whether the subject is clinically deteriorating and unlikely to receive further benefit from continued treatment. The following criteria need to be taken into consideration:

- Absence of clinical symptoms and signs (including worsening of laboratory values) indicating disease progression.
- No decline in ECOG performance status.
- Absence of rapid progression of disease or of progressive tumor at critical anatomical sites (eg, cord compression) requiring urgent alternative medical intervention.

Treatment with cobimetinib beyond progression as monotherapy or as part of the combination with nivolumab and ipilimumab is not permitted.

All decisions to continue treatment beyond progression must be discussed with the BMS Medical Monitor and documented in the study records.

Subjects must be re-consented in order to continue treatment.

Subjects should discontinue study therapy upon evidence of further progression, defined as an additional 10% or greater increase in tumor burden from time of initial progression (including all target lesions and new measurable lesions). Progression in non-target lesions should only be unequivocal as defined and described in [Appendix 3](#) compared to initial progression.

New lesions are considered measurable at the time of initial progression if the longest diameter is at least 10 mm (except for pathological lymph nodes, which must have a short axis of at least 15 mm).

For statistical analyses that include the investigator-assessed progression date, subjects who continue treatment beyond initial investigator-assessed, RECIST 1.1-defined progression will be considered to have investigator-assessed progressive disease at the time of the initial progression event. Subjects who have tumor shrinkage following RECIST-defined progression (ie, immune related response; [Section 5.4.4](#) will be also descriptively summarized separately since these immune responses may be used in determining Go to Stage 2.

4.5.8 Crossover to Arm N-I

Subjects in Arm N may crossover to Arm N-I if all of the criteria defined in [Section 3.1.6](#) are met. Subjects from the SCLC expansion cohort enrolled under or after Amendment 09 are excluded from the crossover option. In case Dose Level 2b has been activated and completed the safety assessment, subjects for cross over will be assigned to Dose Level 2 or Dose Level 2b after discussion between the sponsor and investigator taking into consideration previous safety and efficacy signals at these dose levels and the status of the individual subject planned for cross over.

Before crossover, the investigator should discuss the individual case with the medical monitor and document in the study records.

Subjects must be re-consented prior to crossing over to Arm N-I.

Subjects crossing over to Arm N-I will start treatment at Day 1 Week 1 as described for subjects originally randomized to Arm N-I. Subjects who crossed over and subsequently have an objective response in Arm N-I, will not be considered in respect to the decision making for Arm N-I of proceeding to Stage 2. Subjects in Arm N-I cannot crossover to Arm N.

New lesions are considered measurable at the time of initial progression if the longest diameter is at least 10 mm (except for pathological lymph nodes, which must have a short axis of at least 15 mm).

For statistical analyses that include the investigator-assessed progression date, subjects who crossover after initial investigator-assessed, RECIST 1.1-defined progression will be considered to have investigator-assessed progressive disease at the time of the initial progression event in Arm N. The tumor assessment confirming PD in Arm N will serve as the baseline for tumor assessments in Arm N-I.

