3.1.6 Crossover for Subjects in Arm N

Subjects in Arm N may crossover to Arm N-I if all of the following criteria are met:

- The Safety Evaluation Phase for the N-I regimen has been completed and at least 6 subjects have been exposed to the dose level used for Stage 1 of the N-I regimen. In case Dose Level 2b has been activated and completed the safety assessment, subjects for cross over will be assigned to Dose Level 2 or Dose Level 2b after discussion between the sponsor and investigator taking into consideration previous safety and efficacy signals at these dose levels and the status of the individual subject planned for cross over.
- Subject has further disease progression (investigator-assessed RECIST 1.1-defined progression according to description provided in [Section 4.5.7](#), confirmed at least 4 weeks after the initial tumor assessment showing progression (definition of confirmed progression see [Appendix 3](#))) in the absence of clinical deterioration. For subjects with clear evidence of new or progressing brain metastases a confirmation is not required. These subjects may proceed with brain radiation therapy and, if necessary, with gamma-knife or surgical resection, after having completed the therapy a cross over to Arm N-I can be considered (see [Section 3.4.2.1](#)).
- Subjects with rapidly progressing tumors under nivolumab monotherapy may undergo radiation treatment first before initiation of the cross over after discussion between the sponsor and investigator.
- Subject has not experienced nivolumab related adverse events leading to permanent discontinuation as described in [Section 4.5.5](#).
- Subject is not continuing to derive any clinical benefit from nivolumab single agent therapy as assessed by the investigator which would allow continuation of nivolumab monotherapy (see [Section 4.5.8](#)).
- Subject is not a SCLC patient enrolled based on the Amendment 09 expansion.
- The individual case must be discussed with the medical monitor prior to cross over.

Subjects crossing over to Arm N-I will start treatment at Day 1 Week 1 as described for subjects originally randomized to Arm N-I. Subjects who crossed over and subsequently have an objective response in Arm N-I will not be considered in the decision making for Arm N-I proceeding to Stage 2. Subjects in Arm N-I cannot crossover to Arm N.

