3.4.2.1 Palliative Radiation Therapy

Palliative (limited-field) radiation therapy is permitted for pain control to sites of bone disease or other non-target lesions present at baseline or new lesions. For subjects with new or progressing brain metastases or other lesions, except SCLC subjects from the expansion cohorts under or after Amendment 09, radiation therapy is permitted before a crossover to Arm N-I can be considered.

- 1) Bone and other metastases
 - a) For bone or other disease sites present at baseline or new, the lesion being considered for palliative radiation is not a target lesion.
 - b) The case is discussed with the BMS medical monitor, and the medical monitor agrees that the conditions required to receive palliative radiation are met.
- 2) Brain metastases or other lesions
 - a) Subject is enrolled in-the nivolumab monotherapy arm.
 - b) The case is discussed with the BMS medical monitor, and the medical monitor agrees that the conditions required to receive palliative radiation are met.
 - c) After completion of the brain or other lesions radiation therapy, the BMS Medical Monitor must be consulted before a crossover to Arm N-I can be permitted. Treatment in the crossover arm can only be started after there is no MRI evidence of progression for at least 2 weeks after brain radiation treatment is complete.

3.4.2.2 Surgical Resection or Stereotactic Radiotherapy Following Initial Response or Long-Term Stable Disease

Investigators may choose to resect solitary lesions in subjects with residual or new disease following initial response or stable disease of ≥ 3 months (long-term stable disease) and render the subject free of macroscopic disease. Subjects enrolled in this study may have lesions treated surgically or by stereotactic radiotherapy only following consultation with the Medical Monitor

[REDACTED]

[REDACTED]

[REDACTED]

[REDACTED]

[REDACTED]

[REDACTED]

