1.4 Specifications by methods of measurements

1.4.1 Measurement of lesions

All measurements should be recorded in metric notation (mm). All baseline evaluations should be performed as close as possible to the treatment start and never more than 28 days before the beginning of the treatment.

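### The crossover baseline fixed in 4.5.8 can predate permitted local therapy and may not exist for brain progressors, so shrinkage from that therapy can count as response to nivolumab plus ipilimumab

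*Protocol*

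**What the plan says.** Section 4.5.8 gives a single rule with no exception: "The tumor assessment confirming PD in Arm N will serve as the baseline for tumor assessments in Arm N-I". The document holds two revised protocol texts (07d and 08), and the sentence is the same in both.

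Section 3.1.6 says when that scan is taken and what may happen before crossover:

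- Progression in Arm N must be "confirmed at least 4 weeks after the initial tumor assessment showing progression".
- That requirement is waived for one group: "For subjects with clear evidence of new or progressing brain metastases a confirmation is not required".
- The same group may have local treatment first: "These subjects may proceed with brain radiation therapy and, if necessary, with gamma-knife or surgical resection".
- A second group may too: "Subjects with rapidly progressing tumors under nivolumab monotherapy may undergo radiation treatment first before initiation of the cross over".

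Section 3.4.2.1 repeats the permission for brain metastases and other lesions, outside the SCLC expansion: "radiation therapy is permitted before a crossover to Arm N-I can be considered". Its item 1 (bone and other metastases) requires that the irradiated lesion not be a target lesion. Its item 2 (the pre-crossover route) does not repeat that condition.

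Appendix 3, section 1.4.1, requires baseline evaluations "never more than 28 days before the beginning of the treatment".

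**The concern.** A response is a change from baseline, so the baseline should be the disease as it stands when the regimen starts. Here the baseline is tied to an event in the previous arm, while local treatment may be given between that event and the first N-I dose. Nothing in the protocol resets the baseline after such treatment or says how treated lesions are scored.

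Two things follow. Some subjects may be credited with an N-I response that radiation or surgery produced. Others may have no scan of the kind 4.5.8 names. What is at stake is the response reported for subjects who received N-I after progressing on nivolumab. Section 8.2 defines them as an analysis population, and the assessment schedule singles them out for continued scanning.

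**Working it through.** The protocol gives no figure on this point, so there is none to reproduce. The check is a reading of the sequence, followed by RECIST arithmetic.

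**1. Can local therapy fall between baseline and first N-I dose?** Yes, but it need not. The confirming scan comes at least 4 weeks after first progression. Radiation given between those two scans leaves a post-radiation baseline. Radiation given after the confirming scan leaves a pre-radiation baseline. Section 3.1.6 fixes neither order.

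**2. Can a treated lesion be in the crossover target sum?** Section 3.4.2.1 does not clearly prevent it, because the target-lesion bar stands in item 1 only. There is a second route. Item 1 covers new lesions, and 4.5.8 treats a new lesion of at least 10 mm (15 mm short axis for nodes) as measurable. A lesion that was not a target in Arm N could therefore become one at the crossover baseline.

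**3. How much must be irradiated to produce a partial response (PR) with no drug effect?** Appendix 3 sets PR at a 30% fall in the target sum from baseline. Let *w* be the share of the baseline sum in irradiated lesions, *s* their shrinkage, and *g* the growth of the other target lesions. PR is met when

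w(1 − s) + (1 − w)(1 + g) ≤ 0.70, that is, w ≥ (0.30 + g) / (s + g).

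The protocol gives no value for *s* or *g*. Over an assumed range, the minimum *w* is:

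| Shrinkage s | Others stable (g = 0) | Others grow 10% (g = 0.10) |
|---|---|---|
| 40% | 0.30/0.40 = 75% | 0.40/0.50 = 80% |
| 50% | 0.30/0.50 = 60% | 0.40/0.60 = 66.7% |
| 60% | 0.30/0.60 = 50% | 0.40/0.70 = 57.1% |
| 80% | 0.30/0.80 = 37.5% | 0.40/0.90 = 44.4% |
| 100% | 0.30/1.00 = 30% | 0.40/1.10 = 36.4% |

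Illustration with assumed sizes: targets of 50 mm and 30 mm at the confirming scan, sum 80 mm. The 50 mm lesion is irradiated and halves to 25 mm; the other does not change. The sum is 55 mm, and (55 − 80)/80 = −31.25%, which meets the PR threshold. Against a post-radiation baseline of 55 mm the change is 0%, which is stable disease.

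**4. Does the named scan always exist?** No. Brain progressors may cross over without confirmation, and 4.5.8 offers no substitute. The MRI condition after brain irradiation in 3.4.2.1 governs when treatment may start and is not named as a baseline. This step needs no assumption about shrinkage.

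**5. Is the rule reconciled with the 28-day limit?** No. Where a subject has a confirming scan and then brain irradiation, the two weeks required by 3.4.2.1 use 14 of the 28 days. The radiation course, the medical monitor consultation and re-consent must fit in the other 28 − 14 = 14. The protocol gives no course length, so whether the limit is exceeded cannot be shown. It also does not say which rule yields.

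**6. What does the result feed?** Under 8.3.1, best overall response closes at first RECIST 1.1 progression or subsequent therapy, so post-crossover response is outside the primary ORR. Sections 3.1.6 and 4.5.8 exclude it from the Stage 2 decision. SCLC expansion subjects cannot cross over. What remains is the All Crossover Subjects population in 8.2.

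**The case against.** The strongest reply is about reach. No stated objective or endpoint depends on post-crossover response, and the analysis sections assign the crossover population no ORR. Any such summary may be defined in the SAP. This stands as a limit on importance. It does not repair the baseline, because the protocol itself fixes that and a summary of crossover response would inherit it.

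The second reply is that the protocol has safeguards. Section 3.4.2.1 opens by speaking of non-target and new lesions, and item 2 needs the medical monitor to agree that the conditions for palliative radiation are met. Appendix 3 (1.3.3) says lesions in irradiated areas are usually not measurable unless they have progressed. A reader might infer from item 2 that target lesions may be irradiated. The text does not support that: it is ambiguous, not permissive. But target lesions are not clearly protected either, and the Appendix 3 note does not help when irradiation comes after the baseline scan.

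The third reply is that a false PR needs several things together: treatment after the confirming scan, a treated lesion that dominates the target sum, no offsetting growth or new lesion, and confirmation at least 4 weeks later. That is fair, and the table shows how demanding it is at modest shrinkage. Brain irradiation also leaves extracranial targets alone, so inflation in brain progressors requires a brain lesion among the targets.

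Finally, crossover is closed to cohorts enrolled under or after Amendment 09, so few future subjects may be affected. The definition still governs how crossover scans already taken are scored.

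**Conclusion.** The gap is real and narrow. As written, 4.5.8 can credit shrinkage from local therapy to N-I, names a baseline that brain progressors need not have, and is not reconciled with the 28-day limit. The first part depends on order and lesion choice: therapy after the confirming scan, and treated lesions making up between 30% of the target sum (assumed complete disappearance) and 75% (assumed 40% shrinkage) with other lesions stable. The second and third parts rest on the text alone.

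A reader might go further and infer that the crossover response rate is inflated, or by how many points. The documents do not support this: they give neither the number of crossovers nor how many had local therapy, and they do not fix the order of radiation and scan. Nor do they show that brain progressors lack a confirming scan, only that none is required. Only response, and any duration based on it, in the All Crossover Subjects population is affected. It is worth correcting because the remedy is cheap; it does not threaten the primary result.

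**What to change.** In 4.5.8, replace the baseline sentence with a rule in three parts:

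1. The N-I baseline is the latest available tumor assessment before the first N-I dose, taken after any pre-crossover radiotherapy, gamma-knife or resection where such an assessment exists.
2. Where only a pre-therapy assessment exists, irradiated or resected lesions are left out of the N-I target set.
3. The same rule applies to subjects who cross over without a confirming scan.

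Then reconcile 3.1.6, 3.4.2.1, 4.5.8 and Appendix 3. Say whether the target-lesion condition in item 1 of 3.4.2.1 also governs item 2, and whether the 28-day limit applies to the crossover baseline.

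The cost is a paragraph in 4.5.8, the cross-references and a matching line in the imaging manual. No extra scan is needed. Requiring a fresh scan within 28 days would be tidier, but scans are 12 weeks apart after week 24, so it could add imaging; it is not asked for here. The downside is that a few crossover subjects will have fewer target lesions or become non-evaluable for response. The change concerns measurement only, and no view is taken on whether or when radiotherapy is given.

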4.6 Blinding/Unblinding

Not applicable.

4.7 Treatment Compliance

Treatment compliance will be monitored by drug accountability as well as the subject's medical record and eCRF.

4.8 Destruction of Study Drug

For this study, study drugs (those supplied by BMS or sourced by the investigator) such as partially used study drug containers, vials and syringes may be destroyed on site.

Any unused study drugs can only be destroyed after being inspected and reconciled by the responsible BMS Study Monitor unless study drug containers must be immediately destroyed as required for safety, or to meet local regulations (eg, cytotoxics or biologics).

On-site destruction is allowed provided the following minimal standards are met:

- On-site disposal practices must not expose humans to risks from the drug.
- On-site disposal practices and procedures are in agreement with applicable laws and regulations, including any special requirements for controlled or hazardous substances.
- Written procedures for on-site disposal are available and followed. The procedures must be filed with the site's SOPs and a copy provided to BMS upon request.
- Records are maintained that allow for traceability of each container, including the date disposed of, quantity disposed, and identification of the person disposing the containers. The method of disposal, ie, incinerator, licensed sanitary landfill, or licensed waste disposal vendor must be documented.
- Accountability and disposal records are complete, up-to-date, and available for the Monitor to review throughout the clinical trial period.

If conditions for destruction cannot be met the responsible BMS Study Monitor will make arrangements for return of study drug.

It is the investigator's responsibility to arrange for disposal of all empty containers, provided that procedures for proper disposal have been established according to applicable federal, state, local, and institutional guidelines and procedures, and provided that appropriate records of disposal are kept.

